**Commercial Agents:**

Temozolomide and Lapatinib are commercially available.

## PRÉCIS

### Background:

- Although relatively uncommon, ependymoma can occur at any age group although the tumors of the posterior fossa are much more common in the pediatric population and spinal cord tumors are more common in young to middle age adults. Anaplastic ependymomas are more common in adults
- There have only been a limited number of reports describing chemotherapy treatments for patients with recurrent ependymoma, either low grade or anaplastic. As a consequence, optimal therapy for this group remains unknown. Traditionally, combination chemotherapy regimens have been used, often containing either carboplatin or cisplatin. Many of these treatment programs were associated with a high incidence of moderate to severe toxicity
- Given the paucity of established treatments for recurrent ependymomas in adults, we propose a study that uses a combination of an established cytotoxic agent, temozolamide with a small molecule tyrosine kinase inhibitor. Temozolamide was chosen because it has an established track record in treating primary brain tumors, it has a good safety profile and recent data suggest that certain dosing schedules may modulate tumor cell resistance via the MGMT mechanism. Given the recent studies in glioblastoma that correlate MGMT methylation status with outcome, modulating MGMT activity may have a significant impact on response
- Additionally, we plan to target the ERBB1 and the ERBB2 pathways using lapatinib on a continuous daily dosing schedule

### Objectives:

- To determine the efficacy of the combination of temozolamide and lapatinib in recurrent brain ependymoma and anaplastic ependymoma as measured by median progression-free survival.

[figure not shown]
### Eligibility:

- Histologically proven ependymoma or anaplastic ependymoma. There must be pathologic or imaging confirmation of tumor progression or regrowth.
- Patients must be on a steroid dose that has been stable or decreasing for at least 5 days.
- Karnofsky performance status  $\geq 70$
- Age  $\geq 18$
- No severe, active comorbidity
- No condition that impairs ability to swallow pills

### Design:

- This is a phase II study to determine the efficacy of the combination of temozolomide and lapatinib in recurrent brain ependymoma and anaplastic ependymoma as measured by median progression-free survival.
- Eligible patients will receive 2 cycles of the combination of temozolomide and lapatinib. The temozolomide will be administered at a dose of 125 mg/m^2 as a single daily dose on days 1-7 and 15-21 of a 28-day cycle. The lapatinib will be given as a single daily dose of 1250 mg orally. Patients who do not experience any grade 1 or greater myelotoxicity will be eligible to have the temozolomide dose increased to 150 mg/m^2 as a single daily dose on days 1-7 and 15-21 of a 28-day cycle. The lapatinib dose will not be increased.
- Patients who exhibit response to protocol therapy and have not experienced any significant or intolerable toxicities may continue to receive protocol therapy up to a maximum number of 24 cycles.
- Patients that are showing sustained Complete Response (CR), Partial Response (PR) or Stable Disease (SD) may continue post protocol single agent therapy with lapatinib. Post-protocol lapatinib supply may be obtained through Glaxo Smith-Kline (GSK). Patients on post protocol single agent lapatinib will have follow up visits every 2 months for survival assessment and radiographic evaluation of disease per MRI or CT scan.

## **1 INTRODUCTION**

### **1.1 STUDY OBJECTIVES**

#### **1.1.1 Primary Objective**

To determine the efficacy of the combination of temozolomide and lapatinib in recurrent brain ependymoma and anaplastic ependymoma as measured by median progression-free survival.

#### **1.1.2 Secondary Objectives**

- 1.1.2.1** To determine the efficacy of the combination of lapatinib and temozolomide as measured by objective response in patients with measurable disease.
- 1.1.2.2** To determine the adverse event profile and tolerability of the combination of lapatinib and temozolomide in patients with recurrent ependymoma
- 1.1.2.3** To correlate response, either by objective response or progression-free survival at 12 months with EGFR expression, PTEN expression and MGMT gene promoter methylation status.
- 1.1.2.4** Determine the efficacy of the combination of lapatinib and temozolomide in spinal cord ependymoma as a component of a pilot study.

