- In addition, any subject who develops clinical signs and symptoms of cardiac failure should undergo an LVEF assessment and ECG.

3.7.8 After enrollment on the clinical trial, patients will complete as baseline measures the MDASI-BT or MDASI-SP. The patient will continue to complete the MDASI-BT and/or MDASI-SP at the time of clinical evaluation with MRI as long as the clinical therapy is being administered, unless clinical deterioration makes self-report not possible before that time. The time when patients are unable to complete the self report questionnaires will be used as part of the study analysis. The MDASI-BT and/or MDASI-SP will be completed only by the patient, unless changes in vision or weakness make this difficult. If this occurs, then the caregiver or research assistant may read the questions to the patient or assist with marking the severity number or score as described by the patient. A patient caregiver may complete the questionnaires as a patient-preference proxy if the patient’s deficits preclude self report.

3.7.9 Off treatment follow-up will continue on the following schedule until the patient meets off study criteria.

3.7.9.1 For patients with stable disease or response, MRI surveillance should continue every 2 months for 1 year after treatment completion, then every 3 months for 1 year, then every 4 months for 1 year, then every 6 months until progressive disease is noted, death or lost to follow-up.

3.7.9.2 Patients removed from study treatment for disease progression or treatment-related toxicity should continue to be followed with quarterly (every 3 month) updates of treatment regimens, disease status and survival.

3.7.9.3 Stable disease (SD) patients who develops progression while being followed on the “off treatment follow-up schedule”, will continue with follow-up requirements on the PD off treatment follow-up schedule, until patient meets off study criteria.

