## **5.2 LABORATORY CORRELATES**

Relative to other gliomas, little is known regarding the relevant molecular lesions in ependymoma that contribute to the biologic and clinical behavior of these neoplasms. Activation of the EGFR pathway, as stated above, has been described. In addition, while MGMT methylation has been reported at low frequency, too few cases have been evaluated to lead to firm conclusions. Finally, activation of the PI3K-AKT pathway has not been fully characterized, and its evaluation is justified based on the central role of this pathway in human tumors. Accordingly, molecular testing will include an evaluation of these pathways as well as genome wide screens. Tumor tissue will be evaluated immunohistochemically for expression of EGFR. Activation of the PI3K/AKT pathway will be determined by immunohistochemistry for p-AKT, p-mTOR as well as p-S6. MGMT methylation will be determined using real-time PCR of DNA following bisulfite treatment. Since little is known regarding molecular lesions in ependymoma, genome-wide screens will be performed and will include microarray expression profiling using the Illumina DASL assay (unpublished data from our laboratory suggest that this is feasible in formalin-fixed paraffin embedded tissue). Data from the Cancer Genome Atlas indicate that methylation profiling in glioblastoma is likely to lead to clinically useful biomarkers. Accordingly, methylation profiling using the Illumina Golden Gate Cancer panel, will be performed on these ependymoma samples. These screens as well as the targeted molecular assays will provide the basis for a future molecular classification of ependymoma based on site of origin as well as clinical factors (grade and patient outcome).

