## **8 STATISTICAL CONSIDERATIONS**

The primary goal of this trial will be to assess time to progression, defined as progressive disease, toxicity at a level of severity that precludes the patient continuing on the protocol, or death. Patients will be accrued up to a maximum sample size of 50. Safety monitoring of failure time will be done as follows. Every 2 months, the data from each patient will consist of the time to failure. We define  $T_i$  to be the Time to Progression for the  $i$  th patient

parameterized via a median parameter such that  $T_i | Q_E \sim \text{Exp}(Q_E)$  and  $\text{Median}(T_i) = Q_E$ . We assume that  $Q_E$  has prior distribution  $\text{Inverse Gamma}(a_E, b_E)$  with expectation  $b_E / (a_E - 1)$ . Thus, for each treatment the posterior distribution of  $Q_E | \text{Data}$  is

$\text{Inverse Gamma}(a_E + m_E, b_E + \ln(2) \sum T_i)$  (where  $m_E$  is the number of events in the trial). *A*

*priori*, it is assumed that the median PFS time  $Q_E$  follows an inverse gamma distribution with shape parameter= 2 and scale parameter =17.6761. This prior distribution has median of 10.5 months. The historical median PFS time is represented by  $Q_S$ . In addition,  $Q_S$  is assumed to follow an inverse gamma distribution with shape parameter= 2000 and scale parameter =21000. (This prior also has median of 10.5 months).

The trial will be stopped early if, based on the current data,  $\Pr(Q_E > Q_S + 3.5 | \text{data}) < 0.065$ . That is, the trial will be stopped early if, it is very unlikely that the median time to progression with the experimental therapy (temozolomide and lapatinib) is less than the historical median time to progression for the standard treatment as described in the literature. The rule will be applied every 2 months, with the probability criterion recomputed based on the most recent data available at that time. Based on an anticipated accrual rate of 2.5 patients per month, the trial is expected to complete accrual in 40 months.

To obtain operating characteristics of the early stopping rule, the trial was simulated under three scenarios, which we have summarized in the Table below. The design's operating characteristics are as follows. Each entry in the table is the mean from 2000 simulated trials:

**Table Operating Characteristics.** Maximum sample size 50

Case	Median Time to Progression	Pr(Stop Early)	# Patients (25%,75%)
Scenario 1	2.0	1	16.435 ( 13, 19 )
Scenario 2	7.0	0.896	36.694 ( 27, 50 )

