Scenario 3	10.5	0.173	47.354 ( 50, 50 )
Scenario 4	14.0	0.034	49.054 ( 50, 50 )

We also summarize the median lower and median upper credible intervals for this trial on an assumption of that the data follows an exponential distribution (with median survivals summarized in the Table below). To calculate the expected lower and expected upper credible intervals we simulated progression free survival data (1000 simulations) from exponentially distributed data and assuming observations without events were censored at 48 months (40 months of accrual and 8 months of additional follow-up). For each simulation we recorded the lower (1st decile) and upper (9th decile) credible sets from the posterior distribution of the median PFS parameter. At the end of the simulation we then calculated and recorded below the median 1st decile and median 9th deciles from the vector of recorded deciles obtained from our simulation.

True Median Survival	Median 1 st decile and Median 9 th decile	Credible Limits
10.5 Months		(8.72, 12.50)
14 Months		(11.52, 16.66)

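### Biomarker objective 1.1.2.3 takes PFS only as status at 12 months, which gives up power in a trial of at most 50, and names PTEN expression with no stated measurement

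*Combined protocol and SAP*

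**What the plan says.** Section 1.1.2.3 sets this objective: "To correlate response, either by objective response or progression-free survival at 12 months with EGFR expression, PTEN expression and MGMT gene promoter methylation status". Section 8 gives no test, censoring rule or analysis date for this objective; the only secondary efficacy analysis it describes is the overall response rate.

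On size and calendar, Section 8 states: "Patients will be accrued up to a maximum sample size of 50". It then adds: "Based on an anticipated accrual rate of 2.5 patients per month, the trial is expected to complete accrual in 40 months". The simulation of credible limits for median PFS works by "assuming observations without events were censored at 48 months (40 months of accrual and 8 months of additional follow-up"). Section 3.7.9.1 continues imaging of stable or responding patients after treatment at widening intervals, "then every 6 months until progressive disease is noted, death or lost to follow-up".

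On the markers, Section 1.2.4 lists MGMT methylation, EGFR amplification, EGFR vIII and PI3K pathway activation. Section 5.1.1 names MGMT methylation only. Section 5.2 plans EGFR immunohistochemistry and MGMT PCR, and adds: "Activation of the PI3K/AKT pathway will be determined by immunohistochemistry for p-AKT, p-mTOR as well as p-S6". It also plans two genome-wide screens, a DASL expression array and a methylation panel. PTEN is in none of these lists. It does appear in the rationale in Section 1.2.4, where EGFR-inhibitor response in glioblastoma is said to have tracked EGFR status only when PTEN was present.

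**The concern.** Section 1.2.4 says the correlative work may help define which tumours are best treated with this combination. Two features of the objective weaken it.

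First, a patient who progresses at month 2 and one who progresses at month 11 count the same, as do patients who progress at month 13 and month 40. In a trial of at most 50 patients that is a material loss, and it is avoidable because the primary endpoint already requires the times. A fixed 12-month status also needs 12 months of follow-up on every progression-free patient, and nothing in the plan says the analysis will wait for that or how a patient with less is handled.

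Second, the marker that motivates the hypothesis has no stated source of data. As written, nobody can tell which PTEN variable will be reported.

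**Working it through.** **The plan's own figures.** Accrual time is N divided by rate: 50 / 2.5 = 20 months, not 40. Forty months would need 1.25 patients per month, or 100 patients. The printed 10%-90% credible limits for a true median of 10.5 months are (8.72, 12.50). Simulation with the stated prior gives (8.71, 12.51) if each patient is censored 48 months after their own entry. It gives (8.64, 12.86) if entry is spread over 40 months and the data are cut at month 48. The printed limits therefore fit better without an 8-month minimum follow-up. The plan states no power for objective 1.1.2.3, so there is none to reproduce.

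**Inputs for the power comparison.** N = 50 (Section 8). Prevalence 60% (EGFR in intracranial tumours, Section 1.2.3). Assumed: hazard ratio 2, exponential PFS with medians 9 months (marker-positive) and 18 months (marker-negative), two-sided 0.05, uniform entry, no loss to follow-up.

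**Complete 12-month status, by hand.** With S(t) = 2^(-t/median), S(12) = 2^(-12/9) = 0.397 in 30 positives and 2^(-12/18) = 0.630 in 20 negatives. Overall: 0.6 × 0.397 + 0.4 × 0.630 = 0.490.
- Null SE = √(0.490 × 0.510 × (1/30 + 1/20)) = 0.144.
- Alternative SE = √(0.397 × 0.603/30 + 0.630 × 0.370/20) = 0.140.
- z = (0.233 − 1.96 × 0.144)/0.140 ≈ −0.35, so power is about 0.36.

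**Log-rank, by hand.** Take 20 months of accrual and a cut at month 48, so mean follow-up is 38 months. The progression-free fraction is about 0.6 × 2^(-38/9) + 0.4 × 2^(-38/18) = 0.125, giving about 50 × 0.875 = 43.8 events. Schoenfeld: √(43.8 × 0.6 × 0.4) × ln 2 − 1.96 = 0.29, so power is about 0.61. Simulation gives slightly less.

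**Simulated power:**

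| Accrual / cut (months) | Log-rank | 12-month status, chi-square | Kaplan-Meier difference at 12 months | Status unknown |
|---|---|---|---|---|
| 20 / 48 | 0.57 | 0.37 | 0.40 | 0 |
| 40 / 48 | 0.49 | 0.35 | 0.39 | about 2.75 |

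In the first row every status is known, so the gap of 0.20 comes from dichotomising alone.

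**Sensitivity.** These runs use HR 0.5 (the same ratio in the other direction), pooled median 10.5 months, 40 months of accrual and a cut at 48.
- 50% prevalence: log-rank 0.58 (Schoenfeld: √(39.1 × 0.25) × ln 2 − 1.96 = 0.21, so 0.58), against 0.46 with all statuses known and 0.41 with unknowns dropped.
- 20% prevalence: 0.33 against 0.28 and 0.26.
- 20% prevalence with HR 0.6: 0.20 against 0.19 and 0.18. Here the gap nearly closes because neither method has useful power.

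**Undetermined patients.** These are progression-free patients with under 12 months of potential follow-up. If the cut is 8 months after the last entry, they come from the last 4 months of entry.
- 40-month accrual: 50 × 4/40 = 5 patients. Mean follow-up is 10 months, and S(10) = 0.6 × 2^(-10/9) + 0.4 × 2^(-10/18) = 0.55, so 2.75 are undetermined.
- 20-month accrual: 50 × 4/20 = 10 patients, so 5.5. With a single median of 14 months: 10 × 2^(-10/14) = 6.1.
- 20-month accrual, cut at 48: minimum follow-up is 28 months, so none.

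**Effect of dropping them.** Dropping keeps late entrants who progressed and removes those who did not.
- 40 / 48: 45 × 0.490 / (50 − 2.75) = 0.467, about 2 points low.
- 20 / 28: 40 × 0.490 / (50 − 5.5) = 0.440, about 5 points low.

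**The case against.** The strongest reply is that the objective can be read as a Kaplan-Meier estimate at 12 months, matching the benchmark in Section 1.2.2 (44%, interval 29-68%). That interval is close to symmetric on the log scale (√(0.29 × 0.68) = 0.444), as a survival estimate would be. Such a reading handles censoring and removes the bias. That much stands, but it recovers little power: 0.40 against 0.57.

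A reader might infer that the plan sets a minimum follow-up of 8 months. It does not. The phrase "40 months of accrual and 8 months of additional follow-up" is a simulation assumption for the primary endpoint, it rests on an accrual time that contradicts the stated rate, and Section 3.7.9.1 does not cap imaging follow-up.

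A reader might also infer that late entrants are misclassified. The documents do not support that: they are undetermined, and error arises only under a rule the plan does not state. With 40 months of accrual, a cut at 48 and a median of 10.5 to 14 months, counting them as progression-free would be wrong for about 0.3 patients; counting them as failures, for about 2.3 to 2.8.

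It is fair to say that the objective is secondary, that hazard ratio, medians and alpha are assumed, that 60% applies to EGFR only, and that MGMT methylation is described as infrequent. Log-rank power of 0.5 to 0.6 is itself modest.

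On PTEN, a reader might conclude that it cannot be reported at all. That goes too far, since the DASL array could yield PTEN mRNA. The plan simply does not say it will be used for this. Nor can p-AKT, p-mTOR and p-S6 stand in for PTEN: they are downstream measures, and substituting them would drop the marker on which the rationale rests.

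**Conclusion.** The point holds in two parts.

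Analysing markers against 12-month status costs about 14 to 20 points of power at a hazard ratio of 2 and 60% prevalence, and less at low prevalence or with weaker effects. Most of the loss comes from dichotomising and remains when all statuses are known, so it does not depend on how the follow-up question is settled. Undetermined status is a smaller matter, affecting 0 to about 6 patients, with a downward bias of about 2 to 5 points only if they are dropped. All power figures rest on exponential PFS and the assumptions listed above.

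The PTEN mismatch is textual and needs no assumption: the objective names PTEN expression, and no marker or assay list names a PTEN measurement.

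**What to change.** Restate 1.1.2.3 as the association of each marker with PFS as a time-to-event variable: log-rank test or Cox model, hazard ratio with interval, patients without an event censored at last disease assessment. Keep objective response as a second outcome. Report 12-month PFS by marker only as a Kaplan-Meier estimate. Add this analysis and its data cut-off to Section 8, and reconcile the 40-month accrual with 50 patients at 2.5 per month.

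For PTEN, either state in Section 5.2 that it will be taken from the planned DASL expression profiling, or remove it from the objective. If it is removed, the PI3K/AKT markers can be named as a separate pathway measure, not as a replacement for PTEN.

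The cost is a change of wording and a standard analysis of data already planned, with no extra patients or visits. The small downside is that the hazard ratio assumes proportional hazards. The log-rank test stays valid without that assumption, though it loses power if the curves cross.

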#### **1.1.2.5 Patient Related Outcome Objectives:**

- To evaluate longitudinal changes in symptom measures and determine the impact of the therapy on these parameters.
- To measure symptom burden over the course of therapy to evaluate differences between patients individual symptom severity, overall mean symptom severity, and difference in scores on the interference items between responders and nonresponders.
- To describe the variability of symptom severity longitudinally over the treatment course and follow-up period.

## **1.2 BACKGROUND AND RATIONALE**

### **1.2.1 Ependymoma**

Ependymoma remains a relatively uncommon primary brain tumor in adults. Recent CBTRUS data (1998-2002) compiling incidence of both ependymoma and anaplastic ependymoma in patients age 20 and above reveals a rate of approximately 0.27 per 100,000 population(CBTRUS 2005). Contrast this with glioblastoma where the annual incidence is approximately 9.4 per 100,000. Ependymomas are found throughout the CNS in the supratentorial (ST), posterior fossa (PF), and spinal (SP) compartments and they affect both pediatric and adult populations. The classification of ependymomas is based on the degree of pleomorphism, tumor cells proliferation, cellularity, and tumor infiltration into surrounding brain tissue. The WHO classifies ependymomas into low grade labeled “ependymoma” (also called a “WHO grade II ependymoma) and the more malignant designation “anaplastic ependymoma” (also classified as a “WHO grade III ependymoma”)(Kleihues and Cavenee 2000).

The causes of ependymoma are not known. Although relatively uncommon, the disease can occur at any age group although the tumors of the posterior fossa are much more common in the pediatric population and spinal cord tumors are more common in young to middle age adults. Anaplastic ependymomas are more common in adults. A series of genetic changes have been reported in these tumors, although a wide variability between tumors has been reported. Furthermore, patients can be initially diagnosed with an anaplastic ependymoma or these malignant tumors can develop from the malignant transformation of the lower grade ependymoma. This underscores the importance of genetic changes in the formation of the disease, the biologic behavior including malignant transformation and the potential utilization of these characteristic molecular changes as treatment targets. The variable patterns of histology and clinical presentation of ependymoma, and the separation of pediatric and adult oncology services, have hindered efforts to coordinate clinical trials in this disease. As a result, no new therapeutic approaches have been identified to treat ependymoma during last 20 years and up to 40% of patients remain incurable](Brandes, Cavallo et al. 2005; Merchant and Fouladi 2005).

Currently, the standard therapy for newly diagnosed low-grade ependymoma includes total surgical excision followed by radiation therapy. Complete surgical resection is often not possible because of the location of the tumor and the concern for damage to surrounding eloquent brain during surgery. The situation is even more critical for patients with anaplastic ependymomas because of the higher proliferative rate and greater propensity for tumor infiltration into surrounding normal brain, preventing any possibility of complete tumor removal by surgery. For patients with the more aggressive anaplastic ependymoma, chemotherapy is often administered either before or after the radiation in the hope that infiltrating tumor cells will be eliminated. Unfortunately, even for patients with low-grade ependymoma, survival can be poor when the tumor is not totally surgically resected.

